8.8 Early Termination

Subjects have a right to withdraw from the study at any time. Additionally, the subject may be withdrawn from the study for any reasons: if it is in the best interest of the subject, intercurrent illness, adverse events, or worsening condition. The site investigators or Medical Monitor may request the withdrawal of a subject because of protocol violations, administrative reasons, or any other valid and ethical reasons.

Reasons for subject termination may include, but are not limited to, the following:

- Investigator determination that it is not in the best interest of the subject to continue participation
- Serious adverse events

- Any other safety concerns

In the event of an adverse event in the study eye that is considered by the investigator or Research Monitor to be severe in intensity, the donor tissue will be removed and replaced with fresh cadaveric human cornea donor tissue with or without a keratoprosthesis, discontinuing the patient from further participation in the study.

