6.8 Rescue Medication or Therapy

Subjects who do not retain the cross-linked KPro will be withdrawn from the study and the cornea will be replaced with a cadaver cornea or standard KPro at the physician's discretion.

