10.3 Termination, of Subjects due to Adverse Events

Termination from the study will happen if any of the following occurs:

- Subject's wish to withdraw for any reason.

- Investigator or Research Monitor determination that it is not in the best interest of the subject to continue participation
- KPro removal

In the event an adverse event in the study eye is severe enough to require the donor study tissue to be removed and replaced with fresh cadaveric human cornea donor tissue with or without a keratoprosthesis, the patient will be terminated from further participation in the study. However, prior to termination the patient will be followed for 30 days after replacement surgery to collect any additional event data.

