11. STATISTICAL METHODS/DATA ANALYSIS

11.1 Primary endpoint(s) or outcome measure(s)

- Time from surgery to device loss or replacement

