11.5 Effectiveness Analysis

We will conduct an initial analysis to examine if distributions of baseline characteristics are balanced between the two treatment groups in our randomized study. Standard descriptive statistics will be reported, median (min-max) for numerical variables and frequency count (%) for categorical variables. Comparisons of numerical characteristics between treatment groups

will be conducted using the Mann-Whitney Wilcoxon test. Comparisons of categorical characteristics will be conducted using Chi-square, or Fisher's exact test as appropriate.

Primary Analysis

The primary efficacy analysis will follow an intent-to-treat analysis strategy including all randomized eyes. The major goal of this study is to determine the efficacy of using a collagen cross-linked cornea as a carrier for the Boston Keratoprosthesis in preventing corneal melts and increasing the retention of the keratoprosthesis. The primary endpoint of the efficacy analysis is time from surgery to device loss or replacement. Kaplan-Meier plot of event free survival by treatment groups will be provided and log-rank test will be used to examine if survival curves are significant different between groups. In addition, we will use a proportional hazards regression model to test the effectiveness of using a collagen cross-linked cornea as a carrier for the Boston Keratoprosthesis in preventing corneal melts and increasing the retention of the keratoprosthesis. We will obtain an estimate (95% CI) of the hazard ratio of device loss comparing treatment with control. This framework allows for the control of covariates, which may be unbalanced by chance despite the randomization of treatment assignment. If Kaplan-Meier plots of event free survival by study time, or related plots of log (-log) (survival) indicate violations of the proportional hazards assumption, then weighted log-rank test will be used according to strategies described by Peckova and Fleming.

Secondary Analysis

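### Sections 8.8 and 10.3 allow withdrawal with the device still in place, and neither document says how device status is then recorded or how those eyes are analysed

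*Protocol*

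**What the plan says.** Protocol section 8.8 allows a subject to be withdrawn "if it is in the best interest of the subject, intercurrent illness, adverse events, or worsening condition". It adds that investigators at the sites, and the trial's monitor, "may request the withdrawal of a subject because of protocol violations, administrative reasons, or any other valid and ethical reasons". Section 10.3 has a shorter list. Besides the subject's own wish and KPro removal, it gives "Investigator or Research Monitor determination that it is not in the best interest of the subject to continue participation". None of these grounds, apart from KPro removal, requires the device to be out of the eye.

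Other text takes the subject out at or after device loss:

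- Section 8.8 says that for a study-eye adverse event judged severe, "the donor tissue will be removed and replaced with fresh cadaveric human cornea donor tissue with or without a keratoprosthesis", and the subject then leaves the study.
- Section 6.8 says "Subjects who do not retain the cross-linked KPro will be withdrawn from the study".
- Section 10.3 says that after removal for an adverse event, "prior to termination the patient will be followed for 30 days after replacement surgery to collect any additional event data".

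The primary endpoint (section 11.1, repeated in the SAP) is "Time from surgery to device loss or replacement". On the analysis set, section 11.5 says "The primary efficacy analysis will follow an intent-to-treat analysis strategy including all randomized eyes", and the SAP repeats this. Kaplan-Meier, log-rank and Cox methods are planned for the primary endpoint, and a chi-square or Fisher test for twelve-month retention. Neither document states a censoring rule, or how an eye withdrawn before twelve months enters that test.

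**The concern.** Cross-linking is a single ex-vivo step completed before surgery (sections 6.1 and 8.4). Withdrawing a subject therefore stops no continuing study treatment. Its main effect on the trial is to end observation.

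Section 1.1 describes thinning and melting of the carrier cornea leading to perforation, leakage and extrusion, and section 8.6 treats thinning as a sign of melt. Ocular worsening is thus prognostic for the primary event. If an eye leaves the study for that reason with the device in place, and the device is lost later, the plan has no stated means of capturing the loss. The planned survival methods assume that censoring carries no information about the coming event, and here it could. At stake are the reported retention in each arm, the number of primary events and, if the arms are affected unequally, the hazard ratio.

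**Working it through.** **Step 1: which exits are exposed.** Setting the exit routes beside the endpoint:

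- Severe study-eye event with tissue replaced (8.8): replacement is itself a primary event.
- Non-retention (6.8) and KPro removal (10.3): the event comes at or before exit.
- Adverse event not leading to removal, worsening condition, protocol violation, administrative reason (8.8), or best-interest determination (8.8 and 10.3): the device can still be in place, and no later device status is provided for.

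Only the third group is exposed. With no later data and no rule treating withdrawal as failure, censoring at withdrawal is the default in the planned methods.

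**Step 2: reproduce the design.** Inputs from section 11.3: two-sided alpha 0.05, power 80%, log-rank test, twelve-month follow-up, 4% loss, equal allocation, retention 0.55 vs 0.85.

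- HR = ln(0.85)/ln(0.55) = 0.272.
- Freedman events = (1.960 + 0.842)² × [(1 + 0.272)/(1 − 0.272)]² ≈ 24.
- Mean event probability = (0.45 + 0.15)/2 = 0.30, so 24/0.30 = 80 eyes; 80/0.96 = 83.3, rounded up to 84.

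This matches the stated 84. The other two rows give 90 and 80 against the stated 88 and 82.

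**Step 3: effect of censoring impending losses.** Assume a share f of eyes about to lose the device is withdrawn and censored just before the loss. The observed hazard is then (1 − f) times the true one, so:

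- Kaplan-Meier retention = S^(1−f).
- Events in an arm = (1 − f) × 40.32 × (1 − S), where 84 × 0.96/2 = 40.32 eyes.
- Observed HR = 0.272 × (1 − f in treatment)/(1 − f in control).
- Chance of significance = Φ[√events × (1 − HR)/(1 + HR) − 1.960].

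| f control / treatment | Retention control vs treatment | Difference (points) | HR | Events | Chance of significance |
|---|---|---|---|---|---|
| 0 / 0 | 55.0% vs 85.0% | 30 | 0.272 | 24.2 | 80% |
| 10% / 10% | 58.4% vs 86.4% | 28 | 0.272 | 21.8 | 76% |
| 25% / 25% | 63.9% vs 88.5% | 25 | 0.272 | 18.1 | 68% |
| 50% / 50% | 74.2% vs 92.2% | 18 | 0.272 | 12.1 | 51% |
| 25% / 0 | 63.9% vs 85.0% | 21 | 0.362 | 19.7 | 55% |
| 0 / 25% | 55.0% vs 88.5% | 34 | 0.204 | 22.7 | 88% |

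**Step 4: equal numbers rather than equal shares.** Suppose the 4% loss in each arm consisted entirely of impending failures. Then f = 0.04/0.45 = 0.089 in control and 0.04/0.15 = 0.267 in treatment. Retention would read 0.55^0.911 = 58.0% vs 0.85^0.733 = 88.8%, and HR = 0.272 × 0.733/0.911 = 0.219. The effect would be overstated.

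**Step 5: scale in the actual trial.** The SAP reports 20 removals in 68 eyes, arms pooled. One unrecorded loss would equal 1/20 = 5% of the observed events.

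**The case against.** The strongest reply is that most of the path from melt to failure already ends in a recorded event. Sections 6.8, 8.8 and 10.3 take severe study-eye events, non-retention and removal into device loss or replacement at or before exit. That stands, and it confines the point to discretionary withdrawal with the device in place. With no treatment to stop, investigators may also have little reason to use that route.

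A reader might infer more than the documents support:

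- **That eyes on their way to failure are being censored and retention is overstated.** The documents give no withdrawal count and no censoring rule. Worsening and intercurrent illness need not concern the study eye. The statement has to be conditional.
- **That nothing is collected after withdrawal.** Section 10.1 follows adverse events thought to be drug-related until they resolve or stabilise, with no exception for withdrawn subjects. A footnote in section 8.9 sets a two-year minimum follow-up for everyone. Neither secures device status after withdrawal, but an outright claim that nothing is collected goes too far.
- **That the treatment effect is diluted because more worsening eyes would be controls.** More control failures do not by themselves change the hazard ratio; a larger share withdrawn in control would. Equal shares leave it at 0.272. Masking and look-alike control tissue make a large difference in shares less likely, without excluding it.
- **That this contradicts intent-to-treat.** An eye censored at withdrawal is still analysed in its randomised arm. Intent-to-treat defines the set, but it does not supply the missing outcomes.

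**Conclusion.** The point holds as a limited gap. Withdrawal with the device in place is allowed on grounds that can be prognostic. Neither document secures later device status or states how such eyes are handled in the time-to-event analysis or the twelve-month comparison.

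If those eyes are censored and some were heading for loss, retention is overstated in the affected arm. Equal shares of 10% to 50% would raise apparent control retention by 3 to 19 points and treatment retention by 1 to 7 points. They would leave the hazard ratio unchanged and reduce power from 80% to between 76% and 51%. Unequal shares can move the hazard ratio in either direction.

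Every share is an assumption, as is withdrawal immediately before loss. The true size cannot be determined from the documents and may be small. The change is worth making because it is cheap and each lost event matters with only 20 removals reported.

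**What to change.** In sections 8.8 and 10.3, separate stopping study procedures from ending data collection. The grounds for withdrawal can stay as they are. After withdrawal for any reason, keep recording from standard-of-care records whether the device is in place, lost or replaced, with the date, to the end of follow-up, unless the subject withdraws consent for data collection. Count any later loss or replacement as a primary event.

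In the SAP:

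- censor only at the last known device status;
- state how an eye with unknown status at twelve months enters the retention comparison;
- add a sensitivity analysis, for time to device loss and for twelve-month retention, that counts eyes withdrawn for ocular worsening or an ocular adverse event as failures;
- report withdrawals with the device in place by arm and reason.

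The cost is a few chart checks, one sensitivity analysis and possibly consent wording. Section 8.6 already has staff collecting data from standard-of-care visits, but only after week 52 and without mention of withdrawn subjects, so the provision has to be extended. The SAP reports all 68 eyes as implanted between 2017 and 2020, so the SAP changes and a retrospective status check of withdrawn eyes, where consent allows, are the parts that can still help most.

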6.7 Concomitant Medication

Antibiotics:

First line recommended antibiotic prophylaxis consists of polytrim and vancomycin (14 mg/ml with or without preservatives).

Polytrim should be given as one drop 4 times a day until full graft epithelialization at which point the antibiotic will be decreased to once a day, or as necessary with regard to each patient's needs per the discretion of the study investigator.

In monocular subjects only, fortified vancomycin 14 mg/mL topical drops will be used once a day for the study duration based on the drug availability and upon the discretion of the site principal investigator.

Steroids:

All subjects will receive topical 1% prednisolone acetate drops 4x/day for 6 weeks, 3x/day for 6 weeks, 2x/day for 6 weeks, then 1x/ day for the remainder of the first 6 post-operative months. After 6 months, the subjects can receive pred mild, lotemox, FML or another low dose steroid at least once a day.

Subjects who develop sterile vitritis or another inflammatory condition may require higher doses of steroids and the regimen will be recorded.

Subjects who develop elevated intraocular pressure secondary to steroids should be managed, if possible, by initiating anti-hypertensive therapy as per standard 'glaucoma' care regimens. If this proves inadequate and the intraocular pressure management becomes difficult, the dose (frequency and potency) of the topical corticosteroid will be reduced, especially if there is a

history of steroid-responsiveness. If maximally tolerated medical therapy does not sufficiently control intraocular pressure, alternative approaches to intraocular pressure control should be considered.

NSAIDs:

NSAIDs should be excluded unless needed for cystoid macular edema.

Allergies and Contraindications: The medications can be substituted with alternative equivalents if a patient has an allergy or a contraindication to a specific medication noted above.

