All subjects will receive the standard treatment with corticosteroid and antibiotic eye drops. All subjects will receive topical 1% prednisolone acetate drops 4x/day for 6 weeks, 3x/day for 6 weeks, 2x/day for 6 weeks, then 1x/day for the remainder of the first 6 post-operative months. After 6 months, the subjects can receive pred mild, lotemox, FML or another low dose steroid at least once a day.

Subjects who develop sterile vitritis or another inflammatory condition may require higher doses of steroids and the regimen will be recorded.

Subjects who develop elevated intraocular pressure secondary to steroids should be managed, if possible, by initiating anti-hypertensive therapy as per standard 'glaucoma' care regimens. If this proves inadequate and the intraocular pressure management becomes difficult, the dose (frequency and potency) of the topical corticosteroid will be reduced, especially if there is a history of steroid-responsiveness. If maximally tolerated medical therapy does not sufficiently control intraocular pressure, alternative approaches to intraocular pressure control should be considered.

In addition to standard treatment with corticosteroids, subjects will receive topical antibiotics four times a day until full graft epithelialization at which point the antibiotic will be decreased to once a day, or as necessary with regard to each patient's needs. In monocular subjects only, fortified vancomycin 14 mg/mL topical drops will be used once a day based on the drug availability and upon the discretion of the site principal investigator.

There may be specific features in a given patient that will lead the investigator to use a different post-operative regimen; therefore we will record the use of all medications at each visit.

A bandage contact lens (Kontur Kontakt Lens Co, Inc.) will be worn continuously on the study eye. The diameter, base curve, brand, and replacement schedule will depend on the patient's needs. The presence and type of contact lens used will be recorded at each visit.

All subjects will be instructed in the signs and symptoms of infection or vitritis (decrease in vision; redness, pain or irritation persisting for more than a few hours; painful sensitivity to strong light) are urged to contact their ophthalmologist immediately should they develop such symptoms.

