9.3 Effectiveness Assessments

The efficacy of corneal collagen cross-linking of keratoprosthesis carrier tissue in high-risk keratoprosthesis implantation will be judged using the following parameters and time points:

Primary endpoints or outcome measure(s)

- Time from surgery to device loss or replacement

Secondary endpoints or outcome measure(s)

- Twelve-month retention rate
- Incidence of delayed epithelial healing at day 30 (week 4 visit)
- Cornea thickness metrics measured by AS-OCT; at week(s) 1, 4, 16, 24, 36, and 52.
- Time from surgery to retroprosthetic membrane treatment (laser or surgical interventions)
- Time from surgery to occurrence of vitritis (sterile or infectious)
- Time from surgery to occurrence of ocular surgery to address melt, including partial graft.

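### Protocol 8.8 orders donor-tissue removal for any study-eye adverse event judged severe, while 10.3 orders it only when the event requires removal

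*Protocol*

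**What the plan says.** Protocol 8.8 (Early Termination) closes with a rule for adverse events in the study eye. If the investigator or Research Monitor considers the event "severe in intensity, the donor tissue will be removed and replaced with fresh cadaveric human cornea donor tissue", with or without a new keratoprosthesis, and the effect is described as "discontinuing the patient from further participation in the study". No further condition is attached.

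Protocol 10.3 (Termination of Subjects due to Adverse Events) describes the same action for an event "severe enough to require the donor study tissue to be removed and replaced". It also ends participation, but adds that "prior to termination the patient will be followed for 30 days after replacement surgery to collect any additional event data".

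The primary endpoint is time from surgery to device loss or replacement (Protocol 9.3 and 11.1; SAP, Primary Analysis). Protocol 8.4 describes the donor cornea and the keratoprosthesis being assembled first and then sutured into the eye as a single unit.

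**The concern.** Severity of intensity and need for explantation are different things. An event can be severe and still be treatable without taking out the graft. For such an event 8.8 orders surgery and 10.3 does not.

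Two things are at stake. The first is the patient. Protocol 2.1 describes subjects who are not candidates for a standard corneal transplant, and an investigator who followed 8.8 to the letter would explant an eye that might not need it. The second is the endpoint. Removing the carrier takes the device out with it, so each such removal would be a primary event. It would also enter the SAP composite of removal or melt surgery and, if it fell within the first year, the twelve-month retention rate. The trial asks whether cross-linking prevents melts and so keeps the device in place, and events produced by a severity judgement alone would not bear on that.

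**Working it through.** No arithmetic settles this point; it rests on comparing the two rules.

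| | Protocol 8.8 | Protocol 10.3 |
|---|---|---|
| Trigger | Study-eye event judged severe in intensity | Event severe enough that the tissue has to come out |
| Action | Removal and replacement, mandatory | Removal and replacement, where required |
| Participation | Ends | Ends |
| Follow-up after replacement | Not mentioned | 30 days before termination |

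**Step 1: where the triggers differ.** There are three cases.
- The event is not severe: neither section calls for removal.
- The event is severe and requires removal: both sections lead to removal.
- The event is severe and does not require removal: 8.8 orders removal and 10.3 does not.

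The conflict is confined to the third case.

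**Step 2: is the third case realistic under this plan?** Other sections expect complications to be treated with the device in place.
- Protocol 6.7: "Subjects who develop sterile vitritis or another inflammatory condition may require higher doses of steroids".
- Protocol 8.4: "If maximally tolerated medical therapy does not sufficiently control intraocular pressure, alternative approaches to intraocular pressure control should be considered".
- Protocol 9.3 lists as a separate secondary endpoint "Time from surgery to occurrence of ocular surgery to address melt, including partial graft". The SAP adds its composite partly to capture melts that did not lead to replacement of the device.

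These sections do not grade the events as severe, so they show the intent of the plan indirectly. They fit 10.3 and do not fit a literal 8.8.

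**Step 3: is the trigger defined elsewhere?** Protocol 10.1 has a heading for causality and severity, but the text under it covers causality and seriousness only. No scale for intensity is given there, so the 8.8 trigger rests on individual judgement.

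**Step 4: does follow-up also conflict?** No. Protocol 8.8 is silent on it and 10.3 supplies it, so the 30 days can apply to any removal.

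**Step 5: size.** The SAP (Preliminary Results) gives 20 removals among 68 implanted devices and no reasons. The number made only because of a severity judgement therefore lies between 0 and 20, and nothing in the documents points above 0. The wording could still affect only some of the 68 − 20 = 48 eyes without a recorded removal. The documents do not say how many of those remain in follow-up: implants ran from 2017 to 2020, and follow-up may end at study closure (Protocol 8.6 and 8.9).

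**The case against.** The strongest reply is that this is loose drafting. Protocol 10.3 is the section devoted to termination for adverse events, 8.8 leaves the judgement to a clinician, and the rest of 8.8 is permissive about withdrawal. No surgeon is likely to explant a device only because an event was called severe. Most of this stands, and it is why the point is minor. It does not remove the conflict, because the 8.8 sentence is mandatory and carries no test of clinical need. One could say that an event for which 8.8 orders removal thereby requires it, which would bring 10.3 into play. That reconciles the follow-up, but it would leave the condition in 10.3 with no work to do.

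A reader might infer more than the documents support.
- *That 8.8 loses the 30-day safety data.* It does not say so; it is silent, and 10.3 can be applied alongside it.
- *That Protocol 6.8 is a third conflicting rule.* It states that "Subjects who do not retain the cross-linked KPro will be withdrawn from the study" and leaves the type of replacement to the physician. Both 8.8 and 10.3 leave that choice open too, and a rescue-therapy line need not repeat the 30 days.
- *That a particular diagnosis, such as retinal detachment, would be wrongly explanted.* Protocol 9.1 lists it as an event of special interest, but no section describes its management.

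**Conclusion.** The sentence in 8.8 is wrong as written, and correcting it is a low-priority change that the sponsor could make. It states a mandatory removal rule that 10.3 contradicts for severe events that do not require removal. The likely intent is 10.3.

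The effect on results is unknown and may be zero. A reader might infer that the primary comparison has been diluted or biased, or that power has been lost. The documents do not support that. They give no reasons for the 20 removals and no sign that a site applied 8.8 literally, and any power figure would need an assumed removal rate that they do not supply. Nor would a difference between arms in such removals be bias in itself. If cross-linking changes the rate of severe ocular events, the resulting difference in all-cause device loss is a treatment effect, although one less specific to melt.

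The conclusion rests on the wording of the two sections and on the assumption that removal of the carrier counts as device loss or replacement. The one-unit implantation in 8.4 implies this.

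**What to change.** Replace the last sentence of Protocol 8.8 with a rule to this effect: *donor tissue is removed and replaced only when a study-eye adverse event clinically requires it; the patient is then managed under section 10.3, including 30 days of follow-up after replacement surgery before termination.* The reference to the 30 days is a clarification, since 8.8 does not contradict it.

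Keep all-cause device loss or replacement as the primary analysis. The endpoint, sample size and SAP need no change.

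The cost is one sentence in a protocol amendment. It can help only eyes still in follow-up and cannot alter removals already made. If follow-up has closed, the rewording has no prospective use.
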